1.1 Study Overview

The study ISIS 678354-CS2 is a Phase 2 multicenter, randomized, double-blind, placebo-controlled, dose-ranging study being conducted at approximately 32 sites in the United States and Canada.

Patients ≥ 18 and ≤ 80 years old with elevated plasma triglyceride levels (≥ 200 mg/dL (≥ 2.3 mmol/L) and ≤ 500 mg/dL (≥ 5.7 mmol/L)) and a clinical diagnosis of established CVD, or at high risk for CVD (as defined in the study protocol), will be eligible for enrollment upon meeting the study specific eligibility criteria. Patients will be on standard-of-care preventative therapy for known CVD risk factors as per current guidelines. The study is comprised of the following periods:

- **Screening:** An up to 4 week Screening Period, including an up to 2-week qualification period following an at least 2-week diet stabilization period, where appropriate. Patients on a stable diet known to the investigator and clinically followed at the site may go from Screening to the qualification visit without a 2-week diet stabilization phase.
- **Treatment Period:** Following qualification, up to approximately 100 eligible patients will be randomized in a 1:1:1:1 ratio to one of the 4 dosing cohorts as shown in [Table 1](#), with each cohort having a 4:1 ratio to receive ISIS 678354 or matching volume of placebo, respectively, by SC injection.

Table 1: Study Drug Dosing Information

Cohort	Treatment	Volume to Administer/Dose	# Doses	Total ISIS 678354
A	10 mg ISIS 678354 or placebo (Every 4 weeks)	0.10 mL	≤ 13	≤ 130 mg
B	50 mg ISIS 678354 or placebo (Every 4 weeks)	0.50 mL	≤ 13	≤ 650 mg
C	15 mg ISIS 678354 or placebo (Every 2 weeks)	0.15 mL	≤ 26	≤ 390 mg
D	10 mg ISIS 678354 or placebo (Every week)	0.10 mL	≤ 52	≤ 520 mg

The minimum treatment duration for all patients is 6 months and the maximum is 12 months. The treatment portion of the study will be complete when the last patient reaches 6 months of exposure, at which time patients still receiving Study Drug (ISIS 678354 or placebo) will transition to the Post-Treatment Follow-up Period.

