Safety assessments will be summarized by nominal visit as collected in CRF. For summary tables by nominal visit, only scheduled visits will be used. For multiple records at the nominal (scheduled) visit, the average will be used for continuous values, or the worst will be used for categorical values.

For summary tables of platelet counts by nominal visit, scheduled visits from central lab data and separately, from local lab data will be used. For multiple records at the nominal (scheduled) visit, the average will be used for continuous values, or the worst will be used for categorical values.

3.2.2 *Patient Population Analyzed*

The following analysis sets will be used for the analysis of data as described within each analysis set.

Screened Patients are defined as the patients who sign an informed consent form.

Randomized Patients are defined as the patients who receive a randomization assignment.

Full Analysis Set (FAS): All patients who are randomized and received at least 1 dose of Study Drug (ISIS 678354 or placebo). The FAS represents the practically-feasible intent-to-treat (ITT) population as delineated in International Conference on Harmonisation (ICH) Guideline E9. This population will be used for the analysis of efficacy.

Per Protocol Set (PPS): Subset of the FAS who received prior to the Primary Analysis Timepoint at least 5 monthly doses of Study Drug for patients randomized in Cohorts A and B, or at least 11 every 2-week doses for patients randomized in Cohort C, or at least 22 weekly doses for patients randomized in Cohort D, and who have no major protocol deviations that could compromise the interpretation of efficacy. Major deviations will be determined prior to unblinding for statistical analysis. This population will be used for supportive inferences concerning efficacy.

Safety Set (SS): All patients who are randomized and received at least 1 dose of Study Drug. This population will be used for all safety analyses.

PK Population: All patients who are randomized and received at least 1 dose of ISIS 678354, and have at least 1 evaluable concentration result post first dose. This population will be used for analysis of PK data.

PK Subgroup: A subset of PK population who will undergo additional PK sampling after dose administration on Day 1 and Week 21 (Cohorts A and B) / Week 25 (Cohorts C and D) to evaluate the plasma PK parameters of ISIS 678354.

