3.7 Safety Analyses

All safety analyses will use the Safety Set unless otherwise specified. Unless noted otherwise, denominators for all tables will be number of patients in the SS. Safety endpoints including laboratory assessments and vital signs will be analyzed by nominal visit collected on CRF.

Adverse events, concomitant medications, safety shift tables, and all tables related to safety monitoring/stopping rules will be summarized by 2 periods: on-treatment and on-study. On-treatment assessment is defined as the assessment from the first dose to the last dose of Study Drug plus one dosing interval. For Cohorts A and B, on-treatment period spans time from first dose to the last dose + 28 days; For Cohort C, on-treatment period spans time from first dose to the last dose + 14 days;

For Cohort D, on-treatment period spans time from first dose to the last dose + 7 days. On-study assessment is defined as the assessment from the first dose to the last visit in post-treatment follow-up period.

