3.7.2.1 Treatment Emergent Adverse Events at Injection Site

Treatment Emergent AEs at injection site will follow two definitions:

Definition 1: Local cutaneous reactions at injection site (LCRIS) are defined as injection site erythema, injection site swelling, injection site pruritus, injection site pain, or injection site tenderness that started on the day of injection and persisted for at least two days (i.e. event onset date on the day of injection and resolution date not on the day of injection or the day after injection) will be included. Events on the day of the injection with a missing resolution date will also be included.

Definition 2: Injection Site Reactions (ISR) are defined as any AE with PT or verbatim term containing ‘Injection Site’ that persisted for at least two days (i.e. event onset date on the day of

injection and resolution date not on the day of injection or the day after injection) will be included. Events with a missing resolution date will also be included.

Treatment Emergent LCRIS will be summarized by SOC and PT and by severity in on-treatment period only. Treatment Emergent ISRs will be summarized by SOC and PT and by severity in on-treatment and on-study periods.

Additionally, the following will be summarized using Definition 2 (i.e., ISRs):

- Percentage of injections leading to ISR for overall and preferred term will be summarized using descriptive statistics for on-study period only. Percentage of injections leading to ISR will be calculated as follows for each patient: $(A/B) * 100$, where A = number of injections leading to ISR, and B = total number of injections.
- ISRs by injection location for on-study period only
- Incidence of ISR and time to first ISR for on-study period only
- ISRs by treatment time interval (≤ 13 weeks, $>13-26$ weeks, $>26-39$ weeks, and $>39-52$ weeks) for on-treatment period only

An additional table summarizing ISRs (definition 2) on-treatment by SOC and PT and by severity within cohort will be presented.

3.7.2.2 *Treatment Emergent Flu-Like Reactions*

Treatment Emergent Flu-Like Reactions (FLRs) will follow two definitions:

- Definition 1: TEAEs with either (i) influenza like illness or (ii) at least one of following PTs: pyrexia, feeling hot, or body temperature increased, plus at least two of the following PTs: chills, myalgia, and arthralgia, starting on the day of injection or the next day.

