3.7.2.3 Adverse Events of Special Interest

The TEAEs of bleeding based on the Haemorrhages (SMQ) Export from MedDRA version 20.1 will be summarized by SOC and PT and by severity in on-treatment and on-study period respectively.

The TEAEs of bleeding in presence or absence of concomitant antithrombotic medication (ATC3 Text: Antithrombotic agents) will be summarized by SOC and PT in on-treatment period. The TEAEs of bleeding in presence or absence of concomitant antithrombotic medication will be listed as well.

An additional table summarizing treatment-emergent bleeding AEs on-treatment by SOC and PT within cohort will be presented.

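### The table of injection-site reactions by treatment interval defaults to the whole Safety Set as denominator, so a constant risk would appear to decline after about Week 26

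*Combined protocol and SAP*

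**What the plan says.** SAP 3.7 (Safety Analyses) gives the general rule: "Unless noted otherwise, denominators for all tables will be number of patients in the SS". The population is defined in SAP 3.2.2 (Patient Population Analyzed) without regard to length of treatment: "Safety Set (SS): All patients who are randomized and received at least 1 dose of Study Drug".

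Among the ISR outputs, SAP 3.7.2.1 lists "ISRs by treatment time interval", with cut points at 13, 26, 39 and 52 weeks, restricted to the on-treatment period. It names no denominator for this table. SAP 3.7 defines the restriction: "On-treatment assessment is defined as the assessment from the first dose to the last dose of Study Drug plus one dosing interval".

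On duration, SAP 1.1 says "The minimum treatment duration for all patients is 6 months and the maximum is 12 months" and "The treatment portion of the study will be complete when the last patient reaches 6 months of exposure".

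**The concern.** The on-treatment restriction decides which events are counted. It does not decide which patients are divided by. With no exception written, the default applies, and a patient whose treatment ended at 6 months counts as a patient without an ISR in both later intervals.

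An interval table exists to show whether reactions change with continued dosing. Protocol 2.4 expects these patients to need chronic treatment, and tolerability is part of the primary objective. A decline produced by the denominator could be read as reactions fading with time on drug.

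**Working it through.** **No planned figure to reproduce.** The documents give no ISR rate, no accrual period and no numbers on treatment by interval. The percentages below are scenarios.

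**What follows from the documents alone.** Protocol Appendix A (footnote q in both schedules) makes the Week 25 or Week 27 visit the End of Treatment visit for the last patients, with no dose given there.
- Cohorts A and B: last dose Day 141, window closes on Day 141 + 28 = 169, which is (169 − 1)/7 = 24 weeks.
- Cohort C: Day 169 + 14 = 183. Cohort D: Day 176 + 7 = 183. Both are (183 − 1)/7 = 26 weeks.

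These patients cannot have an on-treatment ISR in the third or fourth interval, yet they remain in the Safety Set. Full treatment in the fourth interval requires a first dose about 26 weeks before the last patient's.

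**Assumptions.** Accrual is uniform over A weeks (26, 39 or 52). Treatment time is min(52, 26 + lag), where lag is the number of weeks by which a patient started before the last patient. There is no early discontinuation. The true risk is constant at 20% per full 13-week interval.

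**Formulas.**
- Weekly hazard: h = −ln(0.80)/13 = 0.2231/13 = 0.0172.
- Mean risk for patients who stop uniformly within an interval: m = 1 − 0.20/0.2231 = 0.1037.
- Displayed, >26-39 weeks: (13/A)·m + (1 − 13/A)·0.20.
- Displayed, >39-52 weeks: (13/A)·m + (1 − 26/A)·0.20.

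For A = 26: 0.5 × 0.1037 + 0.5 × 0.20 = 15.2%, then 0.5 × 0.1037 + 0 = 5.2%.

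| Accrual (weeks) | Share treated beyond Week 39 | Treated time in >39-52, share of full | Displayed ≤13 | Displayed >13-26 | Displayed >26-39 | Displayed >39-52 |
|---|---|---|---|---|---|---|
| 26 | 50% | 25% | 20% | 20% | 15.2% | 5.2% |
| 39 | 67% | 50% | 20% | 20% | 16.8% | 10.1% |
| 52 | 75% | 63% | 20% | 20% | 17.6% | 12.6% |

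An active arm has 100/4 × 4/5 = 20 patients. A true 20% is 4 patients per interval. The table would show 3.0 to 3.5 in the third interval and 1.0 to 2.5 in the fourth.

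**Other true risks, same accrual range.** At 10%, the third interval shows 7.5% to 8.8% and the fourth 2.5% to 6.3%. At 30%, 22.9% to 26.5% and 7.9% to 19.0%.

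**Which denominator repairs it.** Dividing by patients still on treatment at the start of the interval gives 5.2/0.50 = 10.4%, 10.1/0.67 = 15.2% and 12.6/0.75 = 16.8% in >39-52 weeks. The third interval does not change, because in this model everyone enters it. Part of the decline remains because patients leave mid-interval. Per patient-time it nearly vanishes: for A = 26 the rates are about 80, 80, 81 and 83 patients with an event per 100 patient-years.

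A per-injection rate also handles the dosing calendar. With full exposure, the every-4-week schedule gives 4, 3, 3 and 3 injections in the four intervals.

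**The case against.** **The rule is only a default, and denominators will be visible.** A reader might infer that the SAP imposes the Safety Set on every safety output. It does not: the percentage of injections leading to an ISR and the ADA summary use other bases. No such exception is written for the interval table, however. SAP 3.2.2 (Reporting Conventions) requires denominators to be shown, which does not change them. The mock shells it mentions concern laboratory shift and abnormality tables. Unseen shells might carry interval-specific numbers, but nothing in the SAP text asks for them.

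**Other outputs protect the reader.** SAP 3.7.2.1 also plans a per-injection percentage and time to first ISR, and SAP 3.2.5 plans a summary of exposure. These help, but none is split by interval.

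**The affected intervals are secondary.** This stands. The primary safety time point is Week 25 or 27, later analyses are supportive, and the dose-selection text in protocol 10.1.4 names treatment-related SAEs and platelet reductions, not ISR trends. Concurrent randomisation should dilute all arms alike, so comparisons between arms within an interval are largely sound.

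**A steep fall straight after 6 months is not shown.** A reader might infer one. Under 26- to 52-week accrual the third interval loses only 2.4 to 4.8 points of 20; the marked drop comes after Week 39. A printed zero there would need accrual of about 13 weeks. The documents do not exclude that, but SAP 3.3.4 describes enrolment under three successive protocol versions.

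**The bleeding table.** SAP 3.7.2.3 plans a summary of "The TEAEs of bleeding in presence or absence of concomitant antithrombotic medication". A reader might infer that both halves are divided by the whole arm. The text does not establish that. It may classify events rather than patients, and the subgroup frequencies required by SAP 3.2.2 (Reporting Conventions) may already supply the numbers of users and non-users. This supports a clarification only.

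**Conclusion.** The point holds for one table. Applied as written, the SAP 3.7 default makes a constant ISR risk appear to decline after about Week 26, because the design leaves some patients with no treatment, or only partial treatment, in the later intervals. At a true 20% per interval the displayed values would be about 15% to 18% and then 5% to 13%. Those sizes rest on uniform accrual over 26 to 52 weeks, no dropout and a constant hazard. The direction rests only on the staggered end of treatment, and early discontinuation would deepen the decline. The consequence is a misleading time trend in a descriptive table. It is not a biased comparison between arms, and it does not reach the primary safety analysis.

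**What to change.** In SAP 3.7.2.1, state that the interval table will give, for each treatment group and interval, the number of patients treated in that interval and the number of injections given. ISRs should be expressed per injection given in the interval, or per patient-time on treatment, instead of as a percentage of the Safety Set. The per-injection form extends a measure the section already defines. A denominator of patients with at least one injection in the interval is only a partial correction and should not be the sole change.

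In SAP 3.7.2.3, say whether the bleeding table splits patients or classifies events. If it splits patients, state that the denominators are the numbers of antithrombotic users and non-users.

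The cost is a few sentences of SAP text and a small programming change. Dosing and ISR dates are already collected, so no new data are needed.

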3. EXPERIMENTAL PLAN

3.1 Study Design

This is a multicenter, randomized, double-blind, placebo-controlled, dose-ranging study. After an up to 4-week screening period, including an up to 2-week qualification period following an at least a 2-week diet stabilization period, where appropriate, approximately 100 eligible patients will be randomized in a 4:1 ratio to receive ISIS 678354 or placebo. Patients on a stable diet known to the investigator and followed at the site may go from Screening to qualification period without a 2-week diet stabilization phase. Study Drug (ISIS 678354 or placebo) will be administered by subcutaneous (SC) injection every week, every 2 weeks, or every 4 weeks, depending on cohort assignment, for up to 52 weekly doses, up to 26 every 2-week doses, or up to 13 every 4-week doses. Minimum treatment duration is 6 months. Maximum treatment duration is 12 months

The treatment portion of the study will be complete when the last patient reaches 6 months of exposure. All patients still on treatment will then enter a 13-week post-treatment follow-up period. Refer to [Section 3.4.2](#) for additional detail regarding End of Treatment period and scheduling of End of Treatment Visits.

The primary efficacy and safety analysis time point is at Week 25 for patients who received every 4-week dosing (Cohorts A and B) and at Week 27 for patients who received every 2-week or weekly dosing (Cohorts C and D, respectively). For patients continuing treatment beyond the primary analysis time point additional supportive efficacy and safety analyses will be repeated at the completion of Study Drug treatment.

Patients ≥ 18 and ≤ 80 years old with elevated plasma TG levels (≥ 200 mg/dL (≥ 2.3 mmol/L) and ≤ 500 mg/dL (≥ 5.7 mmol/L)) and a clinical diagnosis of CVD or at high risk for CVD are eligible for enrollment upon meeting the study specific eligibility criteria. Patients will be on standard-of-care preventative therapy for known CVD risk factors as per current guidelines.

Clinical diagnosis of CVD is defined as documented coronary artery disease (CAD), stroke, or peripheral artery disease (PAD). A diagnosis of CAD has to be documented by any of the following:

- Angiographic evidence of $\geq 50\%$ stenosis of 1 or more major epicardial coronary arteries
- History of myocardial infarction documented by positive enzymes, and either symptoms of myocardial ischemia, or ECG changes ([Thygesen et al. 2012](#))
- History of coronary revascularization

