10.1 Study Endpoints, Subsets, and Covariates

Efficacy and safety endpoints that will be evaluated after the last patient has completed the primary analysis time point are identified in the following sections.

The primary efficacy and safety analysis time point is at Week 25 for patients who received every 4-week dosing (Cohorts A and B) and at Week 27 for patients who received weekly or biweekly dosing (Cohorts C and D). For patients continuing treatment beyond the primary analysis time point additional supportive efficacy and safety analyses will be repeated at the completion of Study Drug treatment.

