The End of Treatment (EoT) visit for all patients should be scheduled no later than the EoT visit of the last patient to reach 6 months of exposure. The EoT visit should be scheduled to occur at one dosing interval post last dose of Study Drug: one week post last dose for weekly treatment (Cohort D), 2 weeks post last dose for every 2-week treatment (Cohort C), and 4 weeks post last dose for every 4-week treatment (Cohorts A-B). For any patient whose EoT visit would occur later than the EoT visit for the last patient to reach 6 months of exposure, the primary endpoint visit (Week 25 or Week 27 depending on Cohort) will count as the EoT visit.

- **Post-Treatment Follow-up Period:** After the EoT visit has been completed, patients will enter the 13-week post-treatment follow-up period and will return to the Study Center for 3 follow-up visits at 4, 8, and 13 weeks post EoT visit.

1.2 *Objectives*

1.2.1 *Primary Objective*

To evaluate the safety, including tolerability, of ISIS 678354 and to assess the efficacy of different doses and dosing regimens of ISIS 678354 for reduction of serum triglyceride levels in patients with hypertriglyceridemia and established CVD or at a high risk for CVD.

1.2.2 *Secondary Objectives*

To evaluate the efficacy of ISIS 678354 on serum levels of apolipoprotein C-3 (apoC-III), total cholesterol (TC), low density lipoprotein cholesterol (LDL-C), high density lipoprotein cholesterol (HDL-C), non-high density lipoprotein cholesterol (non-HDL-C), very low density lipoprotein cholesterol (VLDL-C), apolipoprotein B100 (apoB) and apolipoprotein A-1 (apoA-I).

To evaluate pharmacokinetics (PK) of ISIS 678354 across different doses and dose regimens in patients with hypertriglyceridemia and established CVD or at a high risk for CVD.

1.2.3 *Exploratory Objectives*

To evaluate the efficacy of ISIS 678354 on serum levels of lipoprotein(a) [Lp(a)], remnant cholesterol, and angiopoietin-like 3 (ANGPTL3).

1.3 *Hypotheses*

The study hypothesis is that ISIS 678354 can significantly reduce the serum triglyceride levels and is well-tolerated for patients with established CVD or at a high risk for CVD.

1.4 *Endpoints*

The primary analysis time point (PAT) is at Week 25 for patients who received every 4-week dosing (Cohorts A and B) and at Week 27 for patients who received weekly or biweekly dosing (Cohorts C

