and D). For patients continuing treatment beyond the PAT additional supportive efficacy and safety analyses will be repeated at the completion of Study Drug treatment. A final analysis will be conducted after all patients have completed their post-treatment follow-up visits.

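### SAP 3.7 plans no overall adverse-event, shift, laboratory-abnormality or stopping-rule table cut at Week 25/27, the protocol's primary safety time point

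*Combined protocol and SAP*

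**What the plan says.** - **Objective.** Safety stands first in the primary objective (Protocol 1.1, SAP 1.2.1).
- **Primary time point.** Protocol 3.1: "The primary efficacy and safety analysis time point is at Week 25 for patients who received every 4-week dosing". Cohorts C and D have Week 27. The synopsis and Protocol 10.1 repeat this (10.1: "The primary efficacy and safety analysis time point is at Week 25").
- **Later analyses.** For patients who continue past that point, Protocol 3.1, Protocol 10.1 and SAP 1.4 all say that "additional supportive efficacy and safety analyses will be repeated at the completion of Study Drug treatment". SAP 1.4 keeps the Week 25/27 time point but no longer labels it a safety time point.
- **Exposure.** SAP 1.1: "The minimum treatment duration for all patients is 6 months and the maximum is 12 months". Treatment stops for everyone once the last patient reaches 6 months.
- **Safety periods.** Under SAP 3.7, adverse events, concomitant medications, shift tables and all monitoring- and stopping-rule tables "will be summarized by 2 periods: on-treatment and on-study". On-treatment runs from first dose to last dose plus one dosing interval (28, 14 or 7 days). On-study runs to the last follow-up visit. SAP 3.7.2 repeats the two periods for adverse events, and 3.7.4 repeats them for shifts and abnormalities. Unless noted otherwise, denominators are Safety Set counts.
- **What is tied to time.** Laboratory tests (including platelets), vital signs and ECG are summarized by nominal visit (SAP 3.7 and 3.7.3 to 3.7.5). Injection site reactions are also tabulated by 13-week interval (SAP 3.7.2.1).

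**The concern.** A supportive repeat at treatment completion presupposes a primary version that stops at Week 25/27. For efficacy, the visit windows in SAP Appendix A supply it. For adverse events, shifts, abnormalities and stopping rules, no period stops there, and the SAP does not say that it replaces the protocol's time point.

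Several protocol safety endpoints are proportions of patients: platelet drops by severity, and liver and renal events by severity (Protocol 10.1.3). A cumulative proportion means little without its time window. Here the window for each patient who completes treatment is set by when that patient enrolled, and the SAP plans no exposure-adjusted adverse-event rates. Dose selection (Protocol 10.1.4) weighs the incidence of treatment-related serious events and of platelet reductions. Those incidences would be read beside a triglyceride effect measured at 6 months, although they cover up to a year in some patients.

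**Working it through.** The plan states no figure to reproduce, so the check has three parts.

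**1. Length of the on-treatment period.** End day = last dose day + dosing interval. The inputs are the dosing schedule in Protocol 8.1 and Appendix A, and the period definition in SAP 3.7.

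| Cohort | Shortest full course ends | Longest course ends | Ratio of lengths |
|---|---|---|---|
| A, B | 141 + 28 = Day 169 | 337 + 28 = Day 365 | 364/168 = 2.17 |
| C | 169 + 14 = Day 183 | 351 + 14 = Day 365 | 364/182 = 2.00 |
| D | 176 + 7 = Day 183 | 358 + 7 = Day 365 | 364/182 = 2.00 |

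The shortest course ends exactly on the primary time point. For patients whose Week 25/27 visit is also their end-of-treatment visit, the on-treatment table already equals the missing one. For the others it adds up to 196 days (A, B) or 182 days (C, D).

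**2. Effect on a reported incidence.** The documents give neither an accrual period nor expected incidences, so both are assumed. Enrolment is uniform over 13, 26 or 39 weeks, and the hazard is constant. Treatment ends when the last patient reaches 26 weeks, with a cap at 52. For simplicity 26 weeks is used for all cohorts.

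Exposure is T = min(26 + U, 52), with U uniform on the accrual period. With h = −ln(1 − p)/26, the reported incidence is 1 − E[exp(−hT)].

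For p = 10%:
- 13 weeks: 13h = 0.0527, and 1 − 0.9 × (1 − e^−0.0527)/0.0527 = 12.3%.
- 26 weeks: 26h = 0.1054, and 1 − 0.9 × 0.1/0.1054 = 14.6%.
- 39 weeks: one third of patients reach the cap, and 1 − (2/3 × 0.854 + 1/3 × 0.81) = 16.1%.

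| Accrual | Mean exposure | 10% reads | 30% reads | 50% reads |
|---|---|---|---|---|
| 13 weeks | 32.5 weeks | 12.3% | 35.9% | 57.7% |
| 26 weeks | 39.0 weeks | 14.6% | 41.1% | 63.9% |
| 39 weeks | 43.3 weeks | 16.1% | 44.4% | 67.6% |

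**3. Effect on the comparison between arms.** Suppose 26 weeks of accrual and arms of 20.
- SD of T = 26/√12 = 7.5 weeks. With independent enrolment dates, the SD of the difference in mean exposure is 7.5 × √(2/20) = 2.4 weeks.
- Permuted blocks lower this. A simulation with five groups of 20 gave 2.38 weeks without blocking, 1.20 with blocks of 50 and 0.50 with blocks of 20. The block size is not stated, so 2.4 is an upper figure.
- At 39 weeks, with a 26-week incidence of 30% (h = 0.0137, event-free fraction 0.7^1.5 = 0.586), 2.4 weeks moves the incidence by about 0.0137 × 2.4 × 0.586 = 1.9 points. The standard error of a difference between two arms of 20 at 41.1% is √(2 × 0.411 × 0.589/20) = 15.6 points.

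**The case against.** A reader might infer that the primary safety analysis is never produced. The documents do not support that. Week 25/27 summaries of laboratory tests, platelets, vital signs and ECG are planned, injection site reactions are cut at 13 and 26 weeks, and SAP 3.2 schedules a report once all patients have completed the primary time point. That last point does not close the gap. It fixes a calendar occasion, and SAP 3.1 takes data up to the last end-of-treatment visit, when early enrollees may have a year of exposure. By-visit summaries also do not give the cumulative proportion of patients with an event.

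A reader might also infer that the varying window biases the comparison of arms, or that chance differences in enrolment date distort it. Neither follows. All cohorts are randomized concurrently in permuted blocks (Protocol 4.2), so exposure should be similar across arms apart from differential discontinuation. The chance imbalance in part 3 is small beside sampling error.

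The strongest remaining points are these:
- Protocol 10.6.2 asks for tabulated adverse events without naming a Week 25/27 cut.
- Treatment beyond 6 months exists for continued safety assessment (Protocol 3.4.2). With about 20 patients per arm, cutting the data would drop events.
- A risk ratio changes with follow-up in any trial. For example, 40% against 20% at 26 weeks (2.0) becomes 53.5% against 28.4% (1.88) at 39 weeks and 64% against 36% (1.78) at 52 weeks under a constant hazard.
- SAP 3.2.5 reports treatment duration by group, so readers can see the exposure.

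These are good reasons to keep the full-exposure tables and to treat the point as one of interpretation. They do not reconcile the SAP with Protocol 3.1 and 10.1, which place primary safety at Week 25/27.

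**Conclusion.** The point holds as a mismatch between the protocol and the SAP. The tables that carry cumulative safety incidence have no version ending at the protocol's primary safety time point, and the only versions planned are those that the protocol calls supportive or that extend into follow-up. The window among patients who complete treatment varies by a factor of 2.0 (Cohorts C, D) to 2.17 (Cohorts A, B); this follows from the stated schedule alone.

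The shift from 10% to about 12% to 16% rests on the assumed accrual and constant hazard. It affects how an incidence reads in every arm and does not show error in the contrast between arms. The consequence is that the reported proportions cannot be taken as 6-month risks and would differ had recruitment been faster or slower. The change is worth making because dose selection uses these proportions, but the trial's conclusions do not stand or fall on it.

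**What to change.** In SAP 3.7, define a primary safety period for each patient: first dose to the Week 25 visit (Cohorts A, B) or the Week 27 visit (Cohorts C, D), or to the end of the on-treatment period if that comes first. Run the adverse-event, shift, laboratory-abnormality and stopping-rule tables on this period and label them the primary safety analysis. Keep the on-treatment and on-study tables as supportive, so that no event is lost from the report.

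The cost is SAP wording, one date cut-off applied to tables already planned, and one more set of tables. No new data are needed. One limit remains: the cut falls at 24 weeks in Cohorts A and B and at 26 weeks in C and D, so pooled placebo averages (168 + 182)/2 = 175 days if its patients divide equally between the two pairs of cohorts. A footnote should say so.

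If the sponsor prefers the on-treatment period as primary, the SAP should state that this departs from Protocol 3.1 and 10.1 and should add exposure-adjusted rates. That avoids the extra tables but gives up the fixed 6-month proportions.
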